6.5.12 Minimal Residual Disease Assessment

Invivoscribe, Inc. will use an assay to determine MRD status after treatment with quizartinib and CPX-351. Minimal residual disease is defined as the minimal traceable persistence of leukemia after treatment.

The assay uses PCR amplification of exons 14 and 15 of FLT3. The PCR primers contain gene-specific regions that are coupled with NGS adaptors designed to identify ≥ 1 FLT3-ITD-containing cell in 10,000 BM cells. An MRD⁻ status will be defined as all results from BM that are negative for the presence of residual clonal cells (<1 FLT3-ITD-containing cell in 10,000 bone marrow cells). A MRD⁺ status will be defined as all results from whole blood or BM that are positive for residual clonal cells (≥ 1 FLT3-ITD-containing cell in 10,000 bone marrow cells). In addition to MRD positivity or negativity, MRD level will be monitored, and the number of residual clonal cells per 10,000 cells will be recorded as well as the total number of cells evaluated in the sample (Levis 2018b).

MRD analysis of FLT3-ITD mutations will occur with all recovery marrows with induction and consolidation cycles (if applicable) Day 35 (+/- 7 days) post-cellular therapy intervention (if applicable), as well as with bone marrow biopsies obtained during the maintenance phase. To monitor for molecular recurrence of disease, BM biopsies and aspirates will be collected at Day 24 (+/- 3 days) Cycles 3, 6, 12, and 24 during the maintenance phase.

7. DRUG FORMULATION, AVAILABILITY, ADMINISTRATION, AND TOXICITY INFORMATION

7.1 Quizartinib

Investigational Product	Dosage Form and Strength	Manufacturer
Quizartinib	20- and 30-mg tablets	Daiichi Sankyo

7.2 Quizartinib Treatment Duration

Patients will receive oral quizartinib once daily, on Days 8-21 of the induction cycle and Days 6-21 of re-induction, if necessary. Administration cannot begin earlier than 24 hours from the last administration of CPX-351. During the consolidation cycles(s), quizartinib begins on Day 6.

Prior to initiation (≤ 24 hour), ECGs in triplicate will be obtained to assess QTcF. If the QTcF is ≤ 450 msec, treatment with quizartinib may proceed (see Section 8). Patients proceeding to an additional cycle of induction as well as those proceeding to consolidation therapy must ensure the FLT3 inhibitor has not been administered before a 4-5 half-life reduction of quizartinib, equivalent to 3 days from the date of last administration.

CONFIDENTIAL

STUDY DRUG: QUIZARTINIB
 PROTOCOL DATE: 10 AUGUST 2020

DEVELOPMENT INNOVATIONS STUDY NUMBER: AML 48
 VERSION 4.0

After induction and consolidation cycles, patients will start maintenance therapy with quizartinib, continuing treatment on Days 1-28 of a 28-day cycle for a total of 24 maintenance cycles.

7.2.1 Labeling, Packaging, and Supply of Quizartinib

Quizartinib tablets will be supplied in high density polyethylene (HDPE) bottles with child-resistant caps.

All study drugs must be kept in a secure place under appropriate storage conditions. Storage conditions for quizartinib are included in the USPI.

7.2.2 Preparation and Administration of Quizartinib

Quizartinib is administered orally. Each 20-mg tablet contains 20 mg quizartinib dihydrochloride (17.7 mg free base) and 200 mg HP β CD. The 20-mg tablets also contain microcrystalline cellulose, magnesium stearate, and Opadry® white film coating. Each 30-mg tablet contains 30 mg quizartinib dihydrochloride (26.5 mg free base) and 300 mg HP β CD. The tablets also contain microcrystalline cellulose, magnesium stearate, and Opadry® yellow film coating.

Preparation and administration instructions will be provided in the quizartinib Investigator's Brochure (IB) and in the USPI.

7.3 CPX-351 Treatment Duration

Patients will be administered CPX-351 (daunorubicin 44 mg/m² IV and cytarabine 100 mg/m² IV) on Days 1, 3, and 5 of the induction cycle. As noted in Section 5, re-induction with CPX-351 (daunorubicin 44 mg/m² IV and cytarabine 100 mg/m² IV) on Days 1 and 3 should occur in patients with an incomplete response in the recovery marrow biopsy, defined as a >50% reduction in the blast count to cellularity ratio compared to the most recent BM biopsy prior to induction. Following induction, a total of 2 cycles of consolidation will occur with CPX-351 (daunorubicin 29 mg/m² IV and cytarabine 65 mg/m² IV) administered on Days 1 and 3.

7.3.1 Labeling, Packaging, and Supply of CPX-351

Daunorubicin and cytarabine liposome for injection is supplied as a sterile, preservative-free, purple, lyophilized cake, in a single-dose vial. Each CPX-351 vial contains 44 mg daunorubicin and 100 mg cytarabine. Store unconstituted CPX-351 vials in a refrigerator at 2°C to 8°C (36°F to 46°F) in an upright position. The vial should be stored in its original carton to protect it from light.

7.3.2 Preparation and Administration of CPX-351

Intravenous infusion of CPX-351 (cytarabine:daunorubicin liposome complex) **requires a central venous catheter or a peripherally inserted central catheter**. CPX-351 is administered over 90 minutes.

Preparation and administration instructions will be provided in the CPX-351 (cytarabine:daunorubicin liposome complex) IB and in the USPI.

CONFIDENTIAL

7.4 Accountability for All Study drugs

The PI (or designee) is responsible for accountability of all used and unused study drug supplies at the site. Development Innovations representatives must be granted access on reasonable request to check drug storage, dispensing procedures, and accountability records.

All study drug inventories must be made available for inspection by the Sponsor or its representatives and regulatory agency inspectors upon request.

At the end of the study, all Development Innovations Drug Accountability Record Form(s) will be completed by the site and sent to the Development Innovations Regulatory Department. Study drug supplies must not be destroyed unless prior approval has been granted by the Sponsor or its representative. Please contact the Development Innovations regarding disposal of any study drug reserves.

7.5 Toxicity of Study Treatments and Study Regimens

7.5.1 Precautions and Risks Associated with Quizartinib

A Phase I dose-finding study using quizartinib as monotherapy in refractory AML demonstrated an ORR of 30% and a median DOR of 13.3 weeks (Cortes et al 2013). All grades of toxicities included nausea (16%), prolonged QT interval (12%), vomiting (11%), and dysgeusia (11%). In a randomized Phase II study using either 30 mg or 60 mg of quizartinib as monotherapy, the patients taking the 30 mg daily dose were found to have a lower incidence of Grade ≥ 2 QTcF prolongation (11%) compared to those who received 60 mg daily (17%). For both dosing groups, other toxicities included diarrhea (18%) and febrile neutropenia (16%) (Schiller et al 2014). Additionally in greater than 10% of patients infection, decreased appetite, hemorrhagic events, abdominal pain, painful swelling, sores in the mouth, rash, asthenia or fatigue, pyrexia, peripheral edema, abnormal hepatic function, mineral deficiency, enzyme deficiency, anemia, and weight loss were reported (Quizartinib Investigator Brochure 2020).

Myelosuppression

Serious AEs of myelosuppression (e.g., febrile aplasia, neutropenia, BM hypocellularity, lymphocytopenia, anemia, thrombocytopenia, and pancytopenia) have been observed, which may result in infections or hemorrhage. Resulting infections (particularly, but not exclusively, fungal and other opportunistic infections, Gram-negative bacterial infections, and bacteremia/septicemia/sepsis) or hemorrhage (e.g., epistaxis, hemoptysis, melena, gastrointestinal bleeding, and hemorrhage intracranial) may be severe, including fatal outcomes. Reports of infection have often been in the context of neutropenia, fever, or both.

QTc Prolongation, Torsades de Pointes

Quizartinib is associated with QTc interval prolongation. QTc interval prolongation may increase the risk of ventricular arrhythmias or TdP.

Regarding review of clinical events potentially associated with QT prolongation (Refer to IB for details):

Completed studies:

CONFIDENTIAL

STUDY DRUG: QUIZARTINIB
PROTOCOL DATE: 10 AUGUST 2020

DEVELOPMENT INNOVATIONS STUDY NUMBER: AML 48
VERSION 4.0

- Of the 241 patients treated with quizartinib in the completed Phase 3 clinical study in adults with relapsed or refractory AML (Study AC220-007), 3.3% were found to have a QTcF interval greater than 500 msec, and 12.4% had an increase from baseline QTcF greater than 60 msec based on central review of ECG data; there were no cases of TdP, cardiac arrest or sudden death reported at the recommended doses (i.e., 30 mg or 60 mg). . In the remaining studies (AC220-002, 2689 CL 2004, CP0001, and 2689-CL-0005): there was 1 subject with TdP (in a phase 2 study while receiving a dose of 90mg; the event resolved after discontinuation of quizartinib, see below for details), 5 subjects with cardiac arrest/cardio-respiratory arrest, and 3 subjects with ventricular tachycardia reported. Overall, after individual review of these events with two external cardiac electrophysiology experts, the 1 event of TdP was associated with QT prolongation, and in 1 of the events of cardiac arrest, a potential arrhythmia event cannot be excluded.
- In the ongoing blinded AC220-A-U302 study in which quizartinib is given in combination with chemotherapy, 6 events of cardiac arrest/cardio-respiratory arrest (5 fatal and 1 non-fatal) and 1 event of sudden death have been reported with quizartinib (See IB section 5.3.6 for further details). Of these, one fatal and one non-fatal cardiac arrest events were due to ventricular fibrillation, and both occurred in the setting of Grade 3 or 4 hypokalemia. These events highlight the importance of monitoring and correcting electrolytes, such as potassium, that may result in QT prolongation as an independent risk factor. The remaining events of fatal cardiac arrest occurred in the setting of other significant concurrent disease (severe sepsis /septic shock, multi-organ failure) with complications and no subject had evidence of QT prolongation at the time of the event (all reported QTcF were <450ms).

Quizartinib should be not be used in subject with long QT syndrome. Quizartinib should be used with caution in patients who are at significant risk of developing QTc interval prolongation. These include patients with uncontrolled or significant cardiovascular disease, congestive heart failure, , hypokalemia and hypomagnesemia, and history of clinically relevant ventricular arrhythmias or TdP and patients receiving concomitant drugs known to prolong the QTc, interval. Electrolytes should be maintained in the normal range. Concomitant use with CYP3A inhibitors may increase quizartinib exposure, and therefore, the dose of quizartinib should be reduced. Specific instructions regarding ECG monitoring, quizartinib dose interruption/reduction and restrictions of concomitant use of other QTc-prolonging drugs are provided in Section 8 and Appendix F.

Quizartinib is an I_{Ks} inhibitor and is associated with QTc prolongation in a dose-dependent manner. As an I_{Ks} inhibitor, quizartinib differs from other agents that can prolong QTc which are I_{Kr} inhibitors. Inhibition of either I_{Ks} and/or I_{Kr} potassium channels may carry increased risk of cardiac events. In Study AC220-007, TEAEs of ECG QT prolonged were reported for 26.6% of patients in the quizartinib arm and 2.1% of patients in the salvage chemotherapy arm. Ten patients (4.1%) had a Grade 3 event, and no patient had a Grade 4 event. In the quizartinib arm, TEAEs of ECG QT prolonged were associated with study drug interruption for 11 (4.6%) patients, dose reduction for 23 (9.5%) patients, and study drug discontinuation for 2 (0.8%) patients (both Grade 2 events).

CONFIDENTIAL

STUDY DRUG: QUIZARTINIB
 PROTOCOL DATE: 10 AUGUST 2020

DEVELOPMENT INNOVATIONS STUDY NUMBER: AML 48
 VERSION 4.0

Eight (3.3%) patients in the quizartinib arm had ECG QTcF values >500 msec (Grade 3 QTcF) by central ECG reading. None of these patients had sequelae (e.g., associated ventricular arrhythmias), and all were able to either continue with the same dose of quizartinib or resume at the same or reduced dose after an interruption with no further occurrences of Grade 3 QTcF. There were no cases of cardiac arrest, sudden death, or TdP in the quizartinib arm.

DS is a severe inflammatory reaction with increased capillary permeability. Symptoms of DS are dyspnea, hypoxia, fever, peripheral edema, hypotension, weight gain, pleuro-pericardial effusion, pulmonary infiltrated, acute renal failure, musculoskeletal pain, and hyperbilirubinemia, peripheral edema, hepatic, renal, or multi-organ dysfunction. Less commonly, DS might present with pulmonary hemorrhage or acute febrile neutrophilic dermatosis.

It is important to promptly recognize the signs and symptoms of DS and implement appropriate treatment. Patients with suspected DS should promptly start treatment with systemic glucocorticoids and hemodynamic monitoring until improvement (Quizartinib Investigator Brochure 2020).

7.5.2 Precautions and Risks Associated with CPX-351

- Cardiotoxicity

The total cumulative dose of non-liposomal daunorubicin >550 mg/m² has been associated with an increased incidence of drug-induced congestive heart failure. In patients who received radiation therapy, the maximum tolerable lifetime dose is 400 mg/m². Calculate maximum lifetime exposure prior to each cycle as shown in Table 1.

Table 1 Cumulative Exposure of Daunorubicin per Cycle of CPX-351

Therapy	Daunorubicin per Dose	Number of Doses per Cycle	Daunorubicin per Cycle
First induction cycle	44 mg/m ²	3	132 mg/m ²
Second induction cycle	44 mg/m ²	2	88 mg/m ²
Each consolidation cycle	29 mg/m ²	2	58 mg/m ²

CONFIDENTIAL

See dose modification/administration guidelines (Appendix G).

- Hemorrhage

12% Grade ≥ 3 (8% in control/7+3 arm), fatal non-disease associated CNS hemorrhage 2% (0.7% in control arm)

- Hypersensitivity

Known in patients receiving cytarabine and daunorubicin. See dose modification/administration guidelines (Appendix G).

- Tissue necrosis

Administer by central venous catheter

- Embryo-fetal toxicity

Counsel to avoid pregnancy, and to use contraception through 6 months after last administration of agent. Because of the potential for serious adverse reactions in breastfed infants, advise lactating women not to breastfeed during treatment with CPX-351. In males, CPX-351 may cause infertility. In male patients wishing to conceive in the future, cryopreservation of sperm prior to administration is recommended.

- Cytopenias

Prolonged thrombocytopenia (<50 beyond Day 42) 28% (versus 12%) in induction and 25% (versus 16%) in consolidation; prolonged neutropenia (ANC <500 beyond Day 42) 17% (versus 3%) in induction and 10% (versus 3%) in consolidation. See dose modification/administration guidelines (Appendix G).

- Chemistry abnormalities

Hyponatremia (14%, 6% with consolidation), hypokalemia (9%, 6% with consolidation), hypoalbuminemia (7%, 2% with consolidation), hyperbilirubinemia (6%, 2% with consolidation), and elevated ALT (5%, 0% with consolidation); all were similar in comparison to 7+3.

The most common serious adverse reactions (incidence $\geq 5\%$) were dyspnea, myocardial toxicity, sepsis, pneumonia, febrile neutropenia, bacteremia and hemorrhage. Adverse reactions led to discontinuation of CPX-351 in 18% of patients (13% in the control arm).

The adverse reactions leading to discontinuation on the CPX-351 arm included prolonged cytopenias, infection, cardiotoxicity, respiratory failure, hemorrhage (GI and CNS), renal insufficiency, colitis, and generalized medical deterioration.

The most common adverse reactions (incidence $\geq 25\%$) in patients on the CPX-351 arm were hemorrhagic events, febrile neutropenia, rash, edema, nausea, mucositis, diarrhea, constipation, musculoskeletal pain, fatigue, abdominal pain, dyspnea, headache, cough, decreased appetite, arrhythmia, pneumonia, bacteremia, chills, sleep disorders, and vomiting.

CONFIDENTIAL

8. DOSE MODIFICATIONS

If toxicity occurs, the toxicity will be graded using the NCI CTCAE Version 5, and appropriate supportive care treatment will be administered to decrease the signs and symptoms thereof. Dose adjustments will be based on the organ system exhibiting the greatest degree of toxicity.

8.1 Criteria and Procedures for Dose Interruptions and Adjustments of Quizartinib

The following are reasons for quizartinib dose reduction or dosing interruption:

- Adverse event: QTcF prolongation, other non-hematologic toxicities, or myelosuppression
- Concomitant administration of a strong CYP3A4 inhibitor

Guidance on dose reductions and interruptions of quizartinib during the induction and consolidation phases as well as the maintenance phase are presented in Table 2 and Table 3, respectively.

The dose of quizartinib will not be reduced lower than 30 mg/day in any phase of the study (not lower than 20 mg/day for patients receiving strong CYP3A4 inhibitors. For AE toxicity management with concomitant strong CYP3A4 inhibitor, the dose of quizartinib will not be reduced lower than 20 mg/day refer to Table 2 for more information).

If quizartinib is interrupted, doses will not be made up.

Table 3 Dose Level Modifications – Induction and Consolidation Phases

Induction and Consolidation Phase				
Full Dose	AE, no concomitant strong CYP3A4 inhibitor	Concomitant strong CYP3A4 inhibitor	AE and concomitant strong CYP3A4 inhibitor	QTcF prolongation
30 mg/day	20 mg/day	20 mg/day	Interrupt ^a	See Section 8.2.1

^aRefer to Appendix F for duration of interruption. Missed doses will not be made up.

Table 4 Dose Level Modifications – Maintenance Phase

Maintenance Phase					
	Full Dose	AE, no concomitant strong CYP3A4 inhibitor	Concomitant strong CYP3A4 inhibitor	AE and concomitant strong CYP3A4 inhibitor	QTcF prolongation
Days 1-14	30 mg/day	20 mg/day	20 mg/day	Interrupt ^a	See Section 8.2.1
Days 15 onward	60 mg/day	40 mg/day ^b	30 mg/day ^c	30 mg/day ^d	See Section 8.2.1

CONFIDENTIAL

^aRefer to Appendix F for duration of interruption. Missed doses will not be made up.

^bCan be further reduced to 30 mg/day, if necessary

^cCan be further reduced to 20 mg/day, if necessary

^dCan be interrupted, if necessary

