5.2.4 Maintenance Phase

The maintenance phase consists of 28-day cycles. Patients will receive quizartinib once daily for a total of 24 cycles or until disease relapse. Maintenance dosing of quizartinib will begin at 30 mg PO once daily on Days 1-14, and if there are no non-hematologic Grade ≥ 3 toxicities and QTcF is maintained ≤ 450 msec, the quizartinib dose will increase to 60 mg/day on Day 15. If consolidation therapy is not advised at all or if only 1 cycle of consolidation is advised based on prolonged toxicities, maintenance therapy will begin 7 days (± 7) after neutrophil recovery (ANC $> 1000/\mu\text{L}$) from the consolidation phase or induction phase.

Patients who proceed to alloHCT or other CT intervention after consolidation will resume quizartinib maintenance no earlier than Day 30 from the intervention or transplant. If ≥ 2 CT interventions (e.g., repeat DLI) are planned after maintenance, a 28-day hold is acceptable, with resumption of quizartinib with the next cycle. If the patient is on quizartinib prior to HCT or CT intervention, quizartinib should be discontinued 7 days prior if a conditioning therapy is utilized. If proceeding to a CT intervention without conditioning therapy (e.g., DLI), quizartinib should be discontinued one day prior to CT intervention.

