6.4.4 Maintenance Phase

The maintenance phase consists of quizartinib monotherapy once daily in 28-day cycles for a total of 24 cycles or until disease relapse. Maintenance dosing of quizartinib PO will begin at 30 mg/day on Days 1-14, and if there are no toxicities and QTcF is maintained ≤ 450 msec, the dose will increase to 60 mg/day on Day 15. The following procedures and tests will be performed at these visits:

- Serum pregnancy test once every 3 cycles during the maintenance phase

6.4.4.1 Cycles 1-24, Days 1 and 15

- Physical examination and vital signs
- ECOG performance status
- AE monitoring
- Concomitant medication review
- CBC and clinical chemistry panel
- BM biopsy and aspirate with FLT3 MRD NGS mutation testing (Day 24 ± 3 days) at Cycle 3, 6, 12 and 24
- ECG and QTcF assessment (if QTcF ≤ 470 msec, continue quizartinib; if QTcF > 470 msec, see Appendix F)

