Appendix F Management of Quizartinib-Associated Adverse Events

QTcF (QT interval corrected with Fridericia's formula) Prolongation

- Grade 1
 - Check magnesium and potassium levels and correct any abnormalities. If possible, stop any medications that may prolong the QTc interval. Continue quizartinib at the same dose.
- Grade 2 (QTcF average of triplicate readings >480 msec)
 - Check magnesium and potassium levels and correct any abnormalities. If possible, stop any medications that may prolong the QTc interval.
 - The dose will be reduced without interruption (See Table 2). Following dose reduction, the quizartinib/placebo dose may be resumed at the previous level in the next cycle if the QTcF has decreased to within 30 msec of baseline or <450 msec but subject must be monitored closely for QT prolongation for the first cycle at the increased dose.
 - If 20 mg/day is the current dose, dosing will be interrupted for up to 14 days. If QTcF returns to within 30 msec of baseline or ≤450 msec within 14 days, treatment may be resumed at 20 mg/day.
- Grade 3 (QTcF average of triplicate readings >500 msec)
 - Check magnesium and potassium levels and correct any abnormalities. If possible, stop any medications that may prolong the QTc interval.
 - Dosing will be interrupted for up to 14 days. If QTcF returns to within 30 msec of baseline or ≤450 msec within 14 days, treatment may be resumed at a reduced dose (See Table 2).
 - If 20 mg/day is the current dose, dosing will be interrupted for up to 14 days. If QTcF returns to within 30 msec of baseline or ≤450 msec within 14 days, treatment may be resumed at 20 mg/day. If Grade 3 event returns, treatment will be discontinued.
- Grade 4 (QTcF >500 msec or >60 msec change from baseline, and Torsade de pointes or polymorphic ventricular tachycardia or signs/symptoms of serious arrhythmia)
 - Treatment will be permanently discontinued.

Differentiation Syndrome

- Patients with suspected differentiation syndrome should promptly start treatment with systemic glucocorticoids and hemodynamic monitoring per local principal investigator or institutional preference until improvement. Treatment should be held until resolution to < Grade 3.

Non-Hematologic Toxicity

CONFIDENTIAL

STUDY DRUG: QUIZARTINIB
PROTOCOL DATE: 10 AUGUST 2020

DEVELOPMENT INNOVATIONS STUDY NUMBER: AML 48
VERSION 4.0

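### Section 8.1 sets a 30 mg/day quizartinib floor that its own dose tables break, and the reduced dose for QTcF prolongation on 60 mg/day is ambiguous

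*Combined protocol and SAP*

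**What the plan says.** **Floor.** Section 8.1 states: "The dose of quizartinib will not be reduced lower than 30 mg/day in any phase of the study". A parenthesis allows 20 mg/day for patients taking a strong CYP3A4 inhibitor and for nobody else.

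**Tables.** The two dose tables in Section 8.1 have a column headed "AE, no concomitant strong CYP3A4 inhibitor". In that column a full dose of 30 mg/day becomes 20 mg/day in induction/consolidation and in maintenance Days 1-14. Section 5.2.4 provides that, subject to toxicity and QTcF, "the quizartinib dose will increase to 60 mg/day on Day 15". From then on the column gives 40 mg/day, and a footnote permits 30. QTcF prolongation has a separate column, and every cell in it refers to Section 8.2.1.

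**Numbering.** The Section 8.1 text says that the dose guidance "during the induction and consolidation phases as well as the maintenance phase are presented in Table 2 and Table 3, respectively". The List of Tables agrees. The captions printed over the tables in the body read Table 3 and Table 4.

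**Appendix F, QTcF.** For Grade 2: "The dose will be reduced without interruption (See Table 2". For Grade 3, after interruption: "treatment may be resumed at a reduced dose (See Table 2". Both grades add "If 20 mg/day is the current dose, dosing will be interrupted for up to 14 days", and neither limits this to inhibitor patients. Section 6.4.4 sends maintenance patients there: "if QTcF > 470 msec, see Appendix F".

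**Appendix F, myelosuppression in maintenance.** The dose may step from 60 to 30 to 20 mg/day. The next sentence interrupts dosing at 30 mg/day, or at 20 mg/day with a strong inhibitor.

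**The concern.** A floor and a dose table are both instructions to the site. Where they disagree, one site will cut to 20 mg/day and another will hold the drug, and each can cite the protocol. Safety and tolerability is a primary objective, so inconsistent dose handling also makes the tolerability data less uniform.

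The QTcF case matters most. Section 1.5 calls the QT effect dose dependent, and Section 7.5.1 reports Grade 2 or higher QTcF prolongation in 11% of patients at 30 mg and 17% at 60 mg. Section 7.5.1 also reports QT-related dose reductions in 23 of 241 quizartinib patients (9.5%) in Study AC220-007. Sites should therefore expect to use the rule. The unclear instruction for 60 mg/day sits at the dose with the higher reported rate.

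**Working it through.** The plan gives no figure to reproduce here, so the check sets the rules side by side.

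**Step 1. Floor against the no-inhibitor adverse-event cells (Section 8.1).**

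| Stage | Full dose | Reduced dose, no strong inhibitor | Against the 30 mg/day floor |
|---|---|---|---|
| Induction/consolidation | 30 | 20 | Breaks it |
| Maintenance Days 1-14 | 30 | 20 | Breaks it |
| Maintenance Day 15 onward | 60 | 40, then 30 | Complies |

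Two of three cells break the floor. The shortfall is (30 - 20)/30 = 33%. In the columns for inhibitor patients, the lowest entry is 20 mg/day or interruption, which complies.

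**Step 2. Floor against the Appendix F QTcF rules at 30 mg/day, no inhibitor.** Grade 2 requires a reduction without interruption. Any reduction from 30 is below 30, so the order breaks the floor whichever table column is consulted. Resuming at a reduced dose after Grade 3 does the same. With the 20 mg and 30 mg tablets listed in Section 7.1, the only whole-tablet dose below 30 is 20. The Appendix F rule for patients already on 20 mg/day shows that its QTcF text expects that dose.

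**Step 3. Floor against the Appendix F myelosuppression rule.** The steps end at 20 mg/day, which breaks the floor without an inhibitor. The following sentence interrupts at 30 mg/day, which respects it. Appendix F therefore does not settle which floor was meant.

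**Step 4. Follow the references for Grade 2-3 QTcF prolongation on 60 mg/day.**

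- Section 6.4.4 leads to Appendix F, which leads to Table 2. By the Section 8.1 text and the List of Tables, that is the induction/consolidation table. It has no 60 mg/day row, and its QTcF cell points to Section 8.2.1.
- The maintenance table's QTcF cell also points to Section 8.2.1.
- Section 8.2.1 covers electrolytes, concomitant drugs and ECG frequency. It gives no dose.

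The references reach no dose in mg/day. Two values can be inferred from elsewhere:

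- 40 mg/day, from the maintenance adverse-event column, because Section 8.1 lists QTcF prolongation among the adverse events that justify reduction. This is a cut of (60 - 40)/60 = 33%.
- 30 mg/day, from the dose level in Section 5.3.2 (60 to 30, or 30 to 20, when a strong inhibitor is started) and the first myelosuppression step. This is a cut of (60 - 30)/60 = 50%.

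**Step 5. Numbering.** No table in the body is captioned Table 2. By the printed captions, Table 3 is the induction/consolidation table, so the reference to Table 3 in the maintenance myelosuppression rule also lands on the wrong table.

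**The case against.** The floor conflict has no good answer. The floor applies in any phase and the column heading excludes inhibitor patients, so neither a phase-specific reading nor the inhibitor exception rescues the two cells.

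The defence of the QTcF rule is stronger. Section 8.1 classes QTcF prolongation as an adverse event and sends maintenance dosing to the maintenance table, so 40 mg/day is a natural reading and the fault may be only a wrong table number. This stands in part: 40 mg/day is plausible. It is not settled, because the table separates QTcF from the adverse-event column, and Section 5.3.2 and the myelosuppression steps both point to 30.

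A reader might infer that a patient with Grade 2-3 prolongation could stay on 60 mg/day, or that the site has no guidance. The documents do not support that. Appendix F requires a reduction at Grade 2, an interruption at Grade 3 and permanent discontinuation at Grade 4. Section 8.2.1 adds close ECG monitoring when QTcF exceeds 480 msec and dosing is changed. Only the size of the reduction is open.

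A reader might also infer that a dose level is defined nowhere. Section 5.3.2 does define one, for starting a strong inhibitor. The accurate point is that its 60-to-30 step differs from the 60-to-40 step in the maintenance table.

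**Conclusion.** The floor conflict holds as a plain contradiction within Section 8.1. It is confined to patients without a strong CYP3A4 inhibitor at stages where the full dose is 30 mg/day, and it makes the Appendix F Grade 2 QTcF order impossible to follow at that dose without breaking the floor. This part rests on no assumption.

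The QTcF point at 60 mg/day is secondary: the reduced dose is ambiguous between 40 and 30 mg/day, with the dose lowered either way. It is tempting to convert this into an expected number of patients. The documents do not say how many will reach 60 mg/day. The 9.5% in Study AC220-007 describes the whole quizartinib arm and not exposure at 60 mg. Patients on a strong inhibitor at enrollment escalate only to 30 mg/day (Section 5.3.2). No count is therefore offered.

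The sample size, the primary response test and the lead-in stopping rule are not affected. The point should be fixed because it concerns a foreseeable cardiac-safety instruction and the correction is small.

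**What to change.** 1. **Choose one floor.** Changing the Section 8.1 sentence to 20 mg/day matches the tables and the Appendix F QTcF rules. If the clinical team wants 30 mg/day, change the two 20 mg/day cells to interruption and rewrite the Appendix F Grade 2 rule. The rules that allow resumption at a reduced dose then also need rewording for patients on 30 mg/day.
2. **Align the myelosuppression text.** Make its steps, and the sentence that interrupts at 30 mg/day, agree with the chosen floor.
3. **Correct the numbering first, then the references.** Renumber the body captions to Table 2 and Table 3, then cite the maintenance table in the Appendix F QTcF and non-hematologic rules. Without renumbering, a reference to Table 3 would lead to the induction/consolidation table.
4. **State the QTcF doses.** Put the reduced dose from 30 and from 60 mg/day in the tables' QTcF cells in place of the reference to Section 8.2.1.
5. **Use one dose ladder** in Section 5.3.2, the maintenance table and Appendix F.

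The cost is a protocol amendment with a clinical decision on the doses and IRB review under Section 14.1. Nothing changes in the sample size or the analysis.
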